The safety of giving continuous glucose sensors (CGS) to adolescents with poor adherence and poor glycemic control was questioned. Adolescents may stop doing finger-stick blood glucose monitoring, they may not calibrate the devices properly and they may make treatment changes based on CGS only rather than finger-stick glucose checks. These human subjects concerns suggest that the proposed study is potentially unsafe and thus unethical. We have addressed these points in multiple ways. The GuardControl trial results ¹ show that youths with baseline HbA_{1c} \geq 8.1% randomized to daily CGS use were treated safely and effectively. Patients who were randomized to the Guardian-RT had mean decrease in HbA_{1c} of 1.0% at 3 months and HbA_{1c} did not increase for controls during the study. Frequency of conventional self monitoring of blood glucose (SMBG) did not decline significantly in either control or CGS patients and remained at 4.6 checks per day at the end of the study, which is above the commonly recommended 4 checks per day. Correspondence from the PI indicates that safety concerns expressed by the study section were not observed in the GuardControl trial. Youths in the two CGS groups had a total of two episodes of severe hypoglycemia, one not during CGS use and one detected by the CGS that did not respond to corrective carbohydrate intake. Diabetic ketoacidosis occurred once in each group. Thus, in a randomized trial enrolling an adolescent sample similar to that proposed here, CGS use decreased HbA_{1c} safely without increasing severe hypoglycemia and it was not associated with significant decreases in the frequency of SMBG. Also, we have summarized the DirecNet studies of the Freestyle Navigator CGS with youths on insulin pump therapy ² and multiple daily injections. ³⁻⁴ These data show that 13 weeks' use of the Navigator decreased mean HbA_{1c} by 0.3% from baseline for insulin pump patients and 0.6% for multiple daily injection patients. When data from only patients with baseline HbA_{1c} \geq 7.5% were analyzed, decreases in HbA_{1c} were more pronounced (0.5% and 0.8%, respectively). Reportable adverse events were negligible and did not differ among those with baseline HbA_{1c} \geq 7.5% versus $<$ 7.5%. Although SMBG frequency declined somewhat more in the DirecNet studies than in the GuardControl trial, the frequency of conventional SMBG in the DirecNet studies was not correlated with HbA_{1c} or severe hypoglycemia; hence, a decrease in SMBG frequency can occur safely in the context of CGS-augmented therapy. Finally, the Juvenile Diabetes Research Foundation's Artificial Pancreas Project, in which [name] is an investigator, has an external Data Safety Monitoring Board that reviews study performance and adverse events every 6 months. The DSMB met recently now that recruitment has ended (n = 451 patients) and, after more than 1,600 patient-months of CGS use, has recommended the continuation of the trial without any required changes in the study protocol or safety monitoring procedures. The GuardControl and DirecNet studies suggest that CGS use as an adjunct to intensive diabetes management can be both therapeutic and safe when used in patients with previously inadequate glycemic control. Also, an external, independent DSMB for the very large JDRF trial has concluded that use of CGS with youths with T1DM is safe and has sufficient therapeutic promise to warrant continuation of the trial.

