Glucose meter with memory All patients with T1DM at these clinics use glucose meters with memory, enabling storage of SMBG results by date and time. Downloading stored data provides a complete record of the patient's SMBG results. Patients will bring their meters to all clinic visits for downloading and discussion of treatment changes. Adolescents will receive a \$10 gift card at each clinic visit if they bring their blood glucose meters with them for downloading, a procedure that has yielded 94% adherence in the FMOD trial.

Downloaded data will yield descriptive statistics and measures of glycemic variability described below. The project will provide SMBG test strips to those without insurance coverage for them.

Continuous Glucose Sensor Diabetes Nurses will be trained by representatives of each CGS company, and with an on-line curriculum that will soon be on the JDRF website.¹⁴⁹ [name], R.N, a Diabetes Nurse in the JDRF Artificial Pancreas Project, will coordinate bi-weekly video-conferences for study nurses before enrollment and monthly case discussions in the first 2 years. Patients in the CGS and CGS+BT groups will select, with the help of diabetes nurses and physicians, the available CGS device that best matches their preferences for use during the study. The devices and supplies will be provided without charge. The same will apply to SC participants during the 3-month Continuation Phase. For the CGS and CGS+BT groups, a 7-day continuous sample of CGS data will be selected randomly from the months prior to the 3-month, 6-month and 9-month study visits to provide profiles for direct comparison to blinded CGS data for the SC group. Adolescents will be paid \$10 for downloading the CGS device and sending the data to the coordinating center monthly. In the DirecNet and JDRF studies, virtually all families have been able to arrange this using either their own computers or one owned by a relative, neighbor or employer. The study will provide a home computer, internet access and training for up to 15 low-SES families.

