Glycemic Variability Kovatchev's Low Blood Glucose Index (LBGI) and High Blood Glucose Index (HBGI) are derived from SMBG values¹⁰⁴⁻¹⁰⁸ and they reflect cumulative deviations of low and high glucose values from the logarithmic midpoint of the normal range. The LBGI and HBGI were validated as predictors of severe hypoglycemia and HbA_{1c}, respectively. The LBGI integrates the weighted values of each BG value that is below 112.5 mg/dl, the logarithmic midpoint of the normal range. The LBGI can be calculated over any interval ranging from a single SMBG result to multiple tests. The HBGI is calculated similarly from BG readings above 112.5 mg/dl. Kovatchev et al. have developed another metric derived from SMBG data, the Average Daily Risk Range (ADRR) and compared prediction of hypoglycemic and hyperglycemic events based on the ADRR with predictions from other indices of variability.¹⁰⁹ The ADRR was the best predictor of both hypoglycemic and hyperglycemic events. The proposed study will permit validation of the ADRR with children, which has not been done. Kovatchev et al. have also validated methods of quantifying glycemic variability for CGS data (Poincare Plots; blood glucose rate of change; Markov Chain interpretations) and these methods also warrant study in children.¹¹⁰⁻¹¹³ We will calculate all of these measures of glycemic variability quarterly from SMBG data (all groups) or CGS data (patients using CGS). For patients randomized to SC, we will calculate these indices based on the 7-day periods of blinded use of a CGS device at Baseline, 3-months, 6-months and 9-months. Comparisons of these measures as predictors of severe hypoglycemia will enable a direct comparison of the utility of SMBG and CGS for predicting those events. Kovatchev and colleagues have also shown that these indices are sensitive to changes in diabetes regimens such as initiation of pramlintide¹¹¹ and islet cell transplantation.¹¹² Kovatchev and Clarke¹¹²⁻¹¹³ have recently reported that the initial effect seen after adding CGS to T1DM therapy is reduced glycemic variability followed by decreased HbA_{1c}. The proposed study will examine whether similar effects occur in our sample during CGS use. [name] consultation provides added assurance that the substantial CGS data to be collected in this study will yield important contributions in the analysis of blood glucose dynamics and the validation of measures of glycemic variability.

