- A 2-week follow-up visit with the diabetes nurse to download the CGS device and further education about responding to CGS data prospectively and retrospectively. Clinical insulin dose adjustment algorithms previously developed and validated in DirecNet studies will be taught to adolescents and parents. A JDRF website will soon be available that will offer additional teaching materials and supports designed for patients using CGS as a component of diabetes management.
- A 1-month follow-up visit with the diabetes nurse to review the family's use of the insulin adjustment algorithms and to evaluate the need for individual refinement of the algorithms.

- The diabetes nurse will be permitted to bring selected adolescents and parents in for interim clinic visits as needed for remedial education to ensure that the adolescent and parent have the requisite knowledge and skills required for deriving optimal benefit from use of the CGS.

Based on the DirecNet Navigator pilot study, we expect HbA_{1c} to decline by approximately 0.3 SD over 9 months to a mean value of about 8.4% for this group.

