Based upon effect sizes achieved in our studies with similar samples, we anticipate that the CGS+BT group will achieve and maintain a mean HbA_{1c} of about 7.4% for effect sizes of 1.2 SD relative to the SC group and 0.8 SD relative to the CGS group. The sampling plan is designed to achieve adequate statistical power to detect effects of this magnitude. A 0.8 SD treatment effect is clinically significant. In terms of glucose variability and risk for hypoglycemia (measured by the LBG1), a recent study of 40 days CGS use (Navigator), 20 days blinded followed by 20 days un-blinded, showed that the LBG1 was reduced by ~0.35 SD during the period of un-blinded use of CGS compared to the blinded use period.¹⁰⁹ We anticipate larger effects in our trial due to its longer duration and enrollment of a sample with more pronounced baseline glycemic variability.

5.9. Data Management and Statistical Analysis Plans. Prior to excusing a parent or youth after completion of any type of data collection, the researcher will ensure that missing items are completed and that errors are corrected. Measures will be recorded on scannable forms for scoring using the OpScan 4.0 optical scanner (NCS-Pearson, Inc., Minneapolis, MN). Data will be double-entered and cross-checked before final computer entry. Data files will be backed up nightly, password-protected and stored on a local area network. Participants will be assigned study ID numbers that will be used rather than names to label completed questionnaires, paper records, etc. All raw data obtained during the project will be stored in locked file cabinets without names recorded on these items. The researchers will maintain a list of ID numbers paired with participants' names and will keep this list in a password-protected computer file separately from other data. Signed informed consent forms, which will contain participants' names, will also be stored separately in locked cabinets. Error checking routines will be created as part of the database application. Weekly reports will be generated for the purpose of monitoring the accrual patterns and for the completeness of data.

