Hypothesis 3b: Improvements in HbA_{1C} during the 9-month Randomized Phase will be mediated by improved scores on the Diabetes Self-Management Profile, Diabetes Problem Solving Interview, Diabetes Responsibility and Conflict Scale, Wiebe Parental Supportive Involvement Interview, and Blood Glucose Monitoring Communication Questionnaire.

5.11. Other planned analyses. The proposed study will yield a rich data set, permitting many interesting analytic directions. Of special interest will be analyses of 1.) Maintenance (CGS and CGS+BT) and replication (SC) of treatment effects during the 3-month Continuation Phase; 2.) Determination of the frequency of CGS use that is associated with improvement in the various indices of glycemic control; 3.) Validation of mathematical models of CGS dynamics as predictors of the occurrence of severe hypoglycemia and HbA_{1C}; 4.) Evaluation of the temporal course of changes in glycemic variability and changes in HbA_{1C} during CGS use; 5.) Descriptive analyses of cost effectiveness as described in section 5.6; 6.) Between-group comparison using survival analysis of the time to first occurrence of severe or moderately severe hypoglycemia; and 7.) Prediction of changes in frequency of CGS use over time based on demographic and behavioral variables.

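### Quarterly variability and quarterly HbA1c are poorly able to show which changes first after CGS is started, although sensor data that could address the early order are already downloaded

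*Combined protocol and SAP*

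**What the plan says.** Section 5.5 (Glycemic Variability) cites a report that, after CGS is added, variability falls first and HbA1c afterwards. It then commits the trial to the same question: "The proposed study will examine whether similar effects occur in our sample during CGS use". Section 5.11 lists it as item 4 of the analyses of special interest: "Evaluation of the temporal course of changes in glycemic variability and changes in HbA_{1C} during CGS use". No time grid or model is given there.

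The frequency rule is in 5.5: "We will calculate all of these measures of glycemic variability quarterly from SMBG data (all groups) or CGS data (patients using CGS". The schedule in 5.7 places these values at months 0, 3, 6, 9 and 12. For sensor users, 5.5 (One-Week Blinded CGS Use) takes a randomly chosen 7-day stretch from the month before each quarterly visit. Central-laboratory HbA1c is drawn at baseline and every 3 months.

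Finer sensor data reach the study anyway. Section 5.8 provides "A 2-week follow-up visit with the diabetes nurse to download the CGS device", and 5.5 pays adolescents for downloading the device and "sending the data to the coordinating center monthly". Section 5.5 also says that the LBGI can be computed over any interval.

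**The concern.** The question is about sequence, and a sequence can be seen only if at least one measurement falls between the two changes. Here both quantities are read on the same 3-month grid. The evidence the plan relies on suggests that both will have moved by the first follow-up reading. If so, variability first, both together and HbA1c first would leave much the same quarterly data, and a conclusion about order would owe more to the spacing of the values than to the patients. At stake is one stated exploratory question. Quarterly HbA1c is as much a cause as quarterly variability.

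**Working it through.** The documents give no power or precision figure for this analysis, so there is none to reproduce. The one plan figure used below is the CGS-arm projection in 5.8, a fall of 0.3 SD. With the SD of 1.2 from 5.13, 0.3 × 1.2 = 0.36 points and 8.8 − 0.36 = 8.44, which agrees with the stated value of about 8.4%.

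**1. Timing in the plan's own sources**
- Variability (5.8): a study of 20 blinded then 20 un-blinded days "showed that the LBG1 was reduced by ~0.35 SD during the period of un-blinded use of CGS".
- HbA1c, GuardControl: daily users "had mean decrease in HbA_{1c} of 1.0% at 3 months" (Section 1). Section 3.7 gives 0.3 points for the SMBG group, so the net fall is 1.0 − 0.3 = 0.7.
- HbA1c, DirecNet Navigator pilots (Section 1): 0.3 points (pump) and 0.6 points (injections) at 13 weeks.
- Later (4.2): only slight further decreases among those who continued, for up to 18 months.

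**2. First post-baseline values**
- Month 3 is about day 91, so the preceding month is about days 61-91.
- Distance from the end of the 20-day period: 61 − 20 = 41 to 91 − 20 = 71 days. As ratios, 61/20 = 3.1 and 91/20 = 4.6.
- The sampled week lies in the month that ends with the first follow-up HbA1c draw, the time by which the cited studies already show a fall.

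**3. How much change is complete by then**

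Assume f(t) = 1 − exp(−t/τ), with τ of 7-30 days for variability and 20-90 days for HbA1c. These constants are assumptions; the documents give none.

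| Day | Variability | HbA1c |
|---|---|---|
| 30 | 63-99% | 28-78% |
| 60 | 86-100% | not computed |
| 91 | 95-100% | 64-99% |

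The curves differ most clearly around day 30, where the plan computes nothing. Even there the ranges overlap, so finer values make the order more visible without guaranteeing it.

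**4. What trace of order remains in quarterly data**

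The main trace would be HbA1c still falling from month 3 to month 6 while variability is flat. The remaining fall is total × [f(182) − f(91)]. Power for a two-sided 0.05 test is approximately 1 − Φ(1.96 − remaining fall/(SD/√n)). Take n = 45 (one arm, 5.13) or 90 (both sensor arms), and an assumed SD of change of 0.6-1.0.
- Total 0.36 points: remaining fall 0.004-0.083, power about 3-26%. Upper end: 0.083/(0.6/√90) = 1.31, and 1 − Φ(0.65) = 0.26.
- Total 1.0 point, τ 60-90 days, SD 0.6, n = 90: remaining fall 0.171-0.231, power 77-96%.
- The same with n = 45: 48-73% at SD 0.6 and 21-34% at SD 1.0.

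**5. What existing downloads could supply**

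91/7 = 13 weeks, so up to about 12 weekly values per sensor user before the month-3 week. Table 1 gives device memories of 30, 60 and 90 days, so monthly downloads can cover the interval, with little margin for the 30-day device.

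**The case against.** The strongest reply is that nothing is lost. Item 4 of 5.11 does not confine itself to quarterly values, the time-stamped sensor data arrive monthly, and a finer grid could be specified at any time before analysis. That stands as far as the sensor data go. But the only stated rule for how often variability is computed is quarterly, and HbA1c stays quarterly in any case. Section 8.6 promises frequent LBGI assessments, but for safety counseling and without an interval.

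A second reply is that HbA1c may keep changing after month 3. In CGS+BT, 5.8 has target behaviors chosen at the end of the 1-month visit and plans refined from month 3, with mean HbA1c projected to reach about 7.4% (8.8 − 7.4 = 1.4 points). The CGS projection is also stated over 9 months. This stands: month-3 variability could then be related to month-6 HbA1c. Such late change would, however, mix the behavioral effect with that of starting CGS, and the question concerns the initial effect.

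A third reply is that the 20 days are the length of a comparison period for one index, the LBGI. They are not a measured onset, and they say nothing of HBGI, ADRR or rate of change. This also stands, so the ratios in the check show how far apart the times lie and do not set a required sampling rate.

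A reader might infer that the order cannot be seen at all, or that no variability data exist before day 91. The documents support neither: the sampled week may begin near day 61, and a large, slow HbA1c effect would leave a detectable trace.

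**Conclusion.** The point holds as a limitation of an exploratory analysis. With both measures quarterly, the planned values are poorly able to show the order of the initial changes, because the plan's own evidence places both at or before the first follow-up values. The exception is a material HbA1c fall after month 3, which is plausible in CGS+BT. For the CGS-arm projection of 0.36 points, the remaining trace has about 3-26% power; under the favorable 1.0-point scenario it reaches 77-96%. Those power figures depend on assumed time constants and SDs. The comparison of dates does not. It rests on the cited timings carrying over to this sample and on the quarterly sensor value using the sampled week.

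A reader might also infer that the glycemic comparisons are compromised. They are not: Hypothesis 1, the sample size and the safety rules do not depend on this question.

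**What to change.** Amend 5.5 and 5.11 item 4 for CGS and CGS+BT:
- Compute the sensor-based variability indices and sensor mean glucose for each week of months 0-3, then every 4 weeks, from the 2-week and monthly downloads. Use only weeks that meet a wear threshold stated in advance.
- Take the blinded run-in week as baseline, and record where its device differs from the one the family later selects.
- Compare the timing of change in variability with that of sensor mean glucose, which has the same resolution.
- Separately, test whether variability change in weeks 1-4 predicts month-3 HbA1c given baseline HbA1c.
- Word the conclusion as order relative to average sensor glycemia and as prediction of HbA1c. Neither analysis dates the onset of HbA1c change, which would need an HbA1c value before month 3.
- Keep the quarterly values for Hypothesis 1.

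The cost is some programming and analysis time, with no new visit, sample or device. Weekly values are noisier, and the 12 or so per user is a ceiling. Wear declined over time in the pilots (3.5), and Section 1 suspends sensor supply when SMBG frequency is inadequate. Pilot wear was, however, higher in the first 4 weeks than in the last 4, and the early weeks matter most here.

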3.4. Cost effectiveness analysis. Cost-effectiveness analysis (CEA) quantifies the added value of medical advances. After ascertaining all costs of each intervention, optimal CEA methods yield an Incremental Cost Effectiveness Ratio (ICER).¹¹⁴⁻¹¹⁶ This requires calculation of Quality-Adjusted Life Years based on health utilities measures (e.g. treatment utilities, experienced utilities, complications utilities, willingness to pay).¹¹⁴ Utilities measures often employ "time-tradeoff" questions asking respondents to indicate how many years in their current health state they would be willing to trade for a given health outcome.¹¹⁴ Many youths may struggle with these abstractions, the methods have not been studied with pediatric diseases and parental proxy for youths' responses has not been validated. A simpler, more affordable approach to cost effectiveness analysis is proposed here. During four selected 2-week periods, all clinicians treating adolescents in this study will record their time devoted to delivery of each adolescent's care, not including time specifically for research tasks. Methods used successfully in [name] prior trial of intensive therapy⁴⁵⁻⁴⁶ will be used in this study. Key drivers of health care costs will be recorded systematically, including hospitalizations, emergency room visits and clinic visits. The collection of these data will permit a basic assessment of the relative costs and therapeutic benefits from CGS use with and without a behavioral intervention relative to standard care and of possible cost savings due to CGS use through reduced health care utilization compared with standard care.

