5.6. Cost-Effectiveness During 4 selected 2-week periods during months 18 through 36, all clinicians will record the time spent in clinical interactions with participants. These "time-sampled" recordings will include all activities related to clinical diabetes care, including clinic appointments, telephone contacts, e-mail exchanges, downloading of glucose meter or CGS devices, interpretation of downloaded data, etc. Activities that are done

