for research purposes only (recruiting, informed consent, questionnaire administration, data transmission) will be excluded. Clinicians will record the duration, nature and purpose of each clinical contact (clinic, phone, e-mail) or other clinical activity (downloading, CGS or meter maintenance, provision of supplies) with each patient using methods employed successfully in [name] intensive therapy trial. The ratio of time dedicated to Intensive Therapy patients to that for Standard Care patients during that study was about 4.5:1 for Diabetes Nurses, 3:1 for Dietitians and Psychologists and 1.3:1 for Physicians. The similarity of these estimates to those reported in the DCCT supports this method as a valid estimate of the degree of health professional time devoted to patients receiving varied interventions, permitting a reasonable derivation of the per-patient incremental costs for the CGS and CGS+BT regimens relative to the SC regimen. *We anticipate that the personnel time for the CGS groups will decline as the study proceeds, but distributing the observation periods throughout the study will yield a valid estimate of the relative personnel requirements for each condition. From these "time-sampled" cost estimates we will extrapolate the per-patient personnel costs of each of three conditions for the entire 9-month Randomized Phase. At quarterly clinic visits, parents will report the occurrence of hospitalizations, emergency room visits, and clinic visits. These reports will be verified by the Diabetes Nurse by medical records checks whenever possible. The costs for hospitalizations, ER visits and clinic visits will be obtained from the involved medical facilities. The retail costs of CGS devices and supplies will be included. Cost effectiveness of the CGS and CGS+BT will be evaluated descriptively both by direct comparison of the estimated costs of SC, CGS and CGS+BT and by reporting the cost per 0.5% improvement in HbA_{1c} during the study for each group. These descriptive analyses will also focus on whether the added costs associated with the CGS regimens are offset by reductions in health care utilization (clinic visits, emergency room visits, hospitalizations) for those groups relative to Standard Care.*

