Continuous Glucose Sensor Plus Behavior Therapy (CGS+BT) Patients randomized to CGS+BT will receive the same education and care as the CGS group. Also, a mental health professional (MHP; e.g. a licensed counselor, post-doctoral fellow, licensed clinical social worker, or psychologist) will deliver a behavioral intervention within a motivational interviewing context that is designed to identify each family's unique behavioral, cognitive or affective barriers and resources pertaining to optimal CGS use, negotiate with the youth and parent a plan addressing the identified targets, and assist the family in implementing, evaluating and possibly refining the selected intervention over the ensuing months. The MHP's role in this study will be very similar to that of the Health Advisor interventionists in the FMOD trial and we will make extensive use of a manual, intervention handouts, telephone contact protocols, intervention plan outlines and other such materials that were developed in that study. *A preliminary draft of the intervention manual appears in the Appendix, to be further refined prior to initiation of the study. Each MHP will receive extensive training in Motivational Interviewing coordinated by our expert consultant, [name].* The MHP will guide the family in preparing an action plan that will include responsibilities of each family member in implementing it, methods of measuring the plan's effectiveness, and a timeframe for evaluation and refinement of the plan. At a minimum, the MHP will telephone the teen and parent 2 weeks before and 2 weeks after diabetes clinic visits to review the family's success with their plan, and trouble-shoot with them any problems they report in implementation of the plan. Like the diabetes educators, the MHP's will be permitted to make appointments with CGS+BT families for more phone contacts and supplemental face-to-face clinic visits as needed to provide the assistance they need to benefit from CGS. MHP's will see each CGS+BT family at every diabetes clinic visit, including with the Diabetes Nurse or Dietitian as needed. MHP's may target for intervention any problem that a family may report that may be impeding the adolescent from using the CGS optimally. *MHP's will document the date, time, duration and content of all telephone and face-to-face encounters with CGS+BT families.* MHP's will be trained to identify certain negative behaviors related to CGS use that could be intervention targets and to recognize instances in which families could benefit from targeting the promotion of positive behaviors rather than on remediation. Below are some CGS-specific target behaviors that MHP's may select with CGS+BT families. Additional target behaviors are likely to be identified during the study.

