The first 12 months will consist of preparatory activities including hiring and training project staff, training study nurses for certification on the CGS devices, insulin pumps and glucose meters to be used during the study, obtaining IRB approval, establishing procedures for data collection, transmission and storage, developing the study procedure manual, curriculum for CGS education and refining the intervention manual for use with the CGS+BT group. Recruitment of participants will begin at about month 12 and will continue until about month 36. Each of the three clinics will be expected to enroll approximately 2-3 patients per month, until the full sample of 150 adolescents has been enrolled at the combined sites. Based on experience with similar trials (JDRF, DirecNet and our Intensive Therapy trial), this pace of recruitment enables efficient completion of the research plan without rapidly overloading the clinical staff with patient encounters, phone contacts and follow-up visits as can easily happen with more rapid recruitment. As has been the case in similar trials, we expect the recruitment rate to taper off gradually. The clinical and educational demands associated with starting patients on CGS devices may exceed that associated with initiation of insulin pump therapy. While there are enough eligible patients, more rapid recruitment could overload the clinical staff and result in sub-optimal delivery of CGS-related education and management supports and compromise the internal validity of the study. The proposed recruitment rate ensures that each clinic will have no more than 30 active study patients concurrently, or about 20 patients in the two CGS groups. We judge the extra demands entailed in CGS-based regimens to be manageable by a 50% FTE Diabetes Nurse and a 10% FTE physician. Data collection will continue through approximately Month 48-51. DSC conference calls will occur once prior to the initiation of recruitment of participants, and then at 6-month intervals beginning 6 months after recruitment commences. A competing renewal application will be prepared and submitted at approximately Month 51. Data cleaning and verification, statistical analysis and dissemination of project results will occur during the final 9-12 months.

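### Section 5.6 would estimate therapist contact cost in CGS+BT from samples catching about 7-9% of contacts, although Section 5.8 has the duration of every contact logged

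*Combined protocol and SAP*

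**What the plan says.** Three parts of the combined protocol and SAP bear on this.

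- **Section 5.6, Cost-Effectiveness.** The source of personnel time is a sample: "During 4 selected 2-week periods during months 18 through 36, all clinicians will record the time spent in clinical interactions with participants". The next step is that "we will extrapolate the per-patient personnel costs of each of three conditions for the entire 9-month Randomized Phase". In support of the method, the section cites staff-time ratios from an earlier intensive therapy trial, including "3:1 for Dietitians and Psychologists". MHPs are not named, either to include or to exempt them.
- **Section 3.4, Cost effectiveness analysis.** The same design is described: "all clinicians treating adolescents in this study will record their time devoted to delivery" of care in selected 2-week periods. One stated purpose is to weigh the costs and benefits of CGS use with and without the behavioral intervention.
- **Section 5.8, Procedures, under CGS+BT.** A separate, continuous record is kept: "MHP's will document the date, time, duration and content of all telephone and face-to-face encounters with CGS+BT families". No section says that this log feeds the cost analysis.

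**The concern.** According to Section 5.8, CGS+BT families receive the same education and care as CGS families, with the MHP added. MHP time is therefore the main planned cost difference between these two arms. Section 5.6, read as written, estimates that time from 8 weeks of sampling, while the trial holds a full record of its telephone and face-to-face part.

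At stake is the precision of one reported quantity: MHP contact hours, and hence MHP contact cost, per CGS+BT family. MHP visits are also front-loaded (baseline, 2 weeks and 1 month, then quarterly). A sample that misses part of the early enrolment period can therefore miss a disproportionate share of the heavier start-up contact.

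**Working it through.** The plan states no sampling share and no precision for the cost estimate, so there is no figure of its own to reproduce.

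**Inputs from the documents**
- Sampling: 4 × 2 = 8 weeks within months 18-36 (Section 5.6). Eighteen months is 78.3 weeks.
- Enrolment (Section 5.15): "Recruitment of participants will begin at about month 12 and will continue until about month 36", at 2-3 patients per clinic per month in three clinics, and "we expect the recruitment rate to taper off gradually". The shape of the taper is not given.
- 50 families per arm (Section 5.13).
- MHP visits at baseline, 2 weeks, 1 month and each quarterly visit; calls 2 weeks before and after clinic visits (Section 5.8). That section gives a total of five encounters, but its list comes to six if month 9 counts. The two should be reconciled; both are tried here.

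**Step 1. Share of Randomized Phase time inside months 18-36, uniform enrolment over months 12-36**
- Enrolled in months 12-18: overlap rises from 3 to 9 months, 6 × 6 = 36.
- Enrolled in months 18-27: full overlap, 9 × 9 = 81.
- Enrolled in months 27-36: overlap falls from 9 to 0 months, 9 × 4.5 = 40.5.
- Total 157.5 of 24 × 9 = 216, or 0.729.

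**Step 2. Share caught**
- 8 / 78.3 = 0.102, and 0.729 × 0.102 = 0.0745, about 7.5%.

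**Step 3. Sensitivity to enrolment shape**

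Contacts are placed at their scheduled times: six visits plus the five calls that fall within 9 months.

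| Enrolment from month 12 | Contacts in months 18-36 | Caught |
|---|---|---|
| Uniform, 24 months | 72.7% | 7.4% |
| Uniform, 20 months (150 / 7.5 per month) | 81.1% | 8.3% |
| Uniform, 16.7 months (150 / 9 per month) | 84.3% | 8.6% |
| Linear taper to half the starting rate, 24 months | 74.4% | 7.6% |
| Linear taper to zero, 24 months | 77.6% | 7.9% |

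Counting five visits and no calls gives 7.7% under uniform 24-month enrolment and 7.1% under the taper to zero. The visit-count discrepancy therefore matters little, and about 7-9% covers the range.

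**Step 4. Counting error alone**
- 11 contacts per family: 50 × 11 = 550; × 0.0743 ≈ 41 caught; 1/√41 = 0.156; 95% = 1.96 × 0.156 = ±31%.
- 12 contacts per family (one call added after baseline): 600 × 0.0745 = 44.7; 1/√44.7 = 0.150; 95% = ±29%.

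**Step 5. Simulation with durations**

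There were 4,000 runs per enrolment shape, with one 2-week window placed at random in each quarter of months 18-36. The documents do not give the extrapolation formula; it was taken as recorded MHP hours / active patient-months × 9. Durations are also assumptions: visits 45 min (SD 15), calls 15 min (SD 7), between-family coefficient of variation 0.3.

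| Enrolment | RMS error | Mean error | 95% range |
|---|---|---|---|
| Uniform, 24 months | 15.5% | -0.6% | -30% to +31% |
| Linear taper to zero | 16.0% | -6.9% | -34% to +22% |
| Uniform, 16.7 months | 15.9% | -7.2% | -33% to +21% |

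Under uniform 24-month enrolment, about 41 contacts from about 32 of 50 families are recorded. With a steep taper or faster enrolment the estimate also runs about 7% low, because fewer of the early visits fall in the windows.

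**Step 6. Absolute scale**
- 6 × 45 + 5 × 15 = 345 min = 5.75 hours per family. A 16% error is 0.16 × 5.75 = 0.9 hour; 30% is 1.7 hours.

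**The case against.** The strongest reply is that this is a deliberate choice in a minor analysis. Section 3.4 opts for a simpler and cheaper approach, Section 5.6 evaluates cost descriptively, and Section 5.11 lists it among other analyses. One method for all staff and arms, used in an earlier trial, is defensible. This stands as a limit on importance. It is not a reason to sample what is already recorded: intervention contact with an MHP exists only in CGS+BT, so counting it in full does not make the treatment of shared staff time uneven.

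It is also fair to say that sampling of MHP time is inferred. Section 5.6 says all clinicians without naming MHPs, and psychologists appear only in the earlier trial's ratios. The wording does cover MHPs and no section exempts them. But Section 5.6 is silent on the log; it does not rule it out.

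Three stronger readings are tempting, and the documents do not support them.

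- **That the log already holds the exact MHP cost.** It names telephone and face-to-face encounters only. Section 5.8 also allows MHP e-mail, which Section 5.6 counts as clinical time, and preparation is not named in the log.
- **That using the log would free the CGS+BT versus CGS cost difference of sampling error.** Nurse, dietitian and physician time stays sampled in both arms. The incremental costs the plan names are, moreover, relative to Standard Care; CGS+BT versus CGS enters through the direct comparison of the three arms.
- **That sampled contacts cluster in a few start-up families, so the true error is much larger.** This is not shown. About 41 contacts from 32 families is 1.3 per family, and the simulated error with family variation (about 16%) is close to the counting error (about 15%).

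**Conclusion.** The point holds for MHP contact time. The plan as written would estimate it from a small sample when a complete log of telephone and face-to-face encounters will exist. The size of the error rests on the enrolment calendar in Section 5.15 and on assumed contact counts, durations and extrapolation formula; other durations would move it.

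The sampling error on this component is avoidable; that on other staff time is not removed by the log. Nothing here shows that a reported cost conclusion would change. This is an inexpensive gain in precision and a low-priority point.

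**What to change.** In Section 5.6, state that MHP telephone and face-to-face time will be costed for each CGS+BT family from the complete encounter log, over the dates of that family's 9-month Randomized Phase. State that these logged encounters replace any MHP encounters recorded in the 2-week samples, so that nothing is counted twice. Keep the samples for nurses, dietitians and physicians in all arms, and for MHP e-mail, preparation and notes.

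The cost is a sentence or two in Section 5.6 and data entry of a log already kept. Because the log records content, any entry that is not clinical can be set aside; Section 5.8 already keeps MHPs out of recruitment and data collection.
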